- 4.) the time necessary for return to work in patients between 18 and 60 years?

Trial design

The study design is a parallel group, randomized controlled trial with open allocation including all patients with calcaneus fractures independent of kind of initial therapy.

Methods: Participants, interventions, and outcomes

Study setting

All patients treated for calcaneus fracture (DS920* 'Fraktur af hælben' according to the Danish SKS-browser) at the University Hospital Odense are prospectively screened for eligibility and included in the trial, if they fulfil the inclusion criteria as listed below. The follow-up period is 6 months.

Eligibility criteria

In Denmark, the treatment of calcaneus fractures is regarded as highly specialized, wherefore both decision-making and operations are done for the whole Region of Southern Denmark in the Department of Orthopaedics and Traumatology at the University Hospital Odense. Therefore, patients are screened by consultants of the local trauma section.

Inclusion criteria:

- Fracture of the calcaneus, which is classifiable according to the Sanders' classification (excludes avulsion fractures)
- Being able to understand Danish or English and answer the questionnaires
- Informed consent
- Age between 18 and 65 years

Exclusion criteria:

- Pathological fractures
- Immature skeletal system
- Other fractures with influence on weight-bearing
- A soft-tissue situation not allowing the equipment with a 'Settner shoe' within 3 weeks after treatment (either decision-making for non-operative therapy or open reduction and internal fixation)

Acquiring patient consent

The participants will be introduced to the study by the medical personnel in a room, where they will not be disturbed. It will be assured that patients are allowed (if they wish) to be introduced to the study accompanied by a family member or any other person(s) selected by the patient. Patients will be given an oral overview of the purpose of the study, a participant information document describing the study and potential risk together with a patient consent form, which the patients will sign if they decide to participate in the study. The patient can resign from participating in the study without giving a reason and without any consequences. Patients are included after the operation or after decision for non-operative therapy, but before discharge.

Interventions

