After operation or decision for non-operative therapy, the schedule for the 2 groups are defined as follows:

Group 1 (treatment without 'Settner shoe'):

- mobilization without weight bearing for 6 weeks starting with the day of either decision-making for non-operative therapy or open reduction and internal fixation, if needed a cast or another kind of orthosis as a Static Walker are applied, then 4 weeks 15-20 kg, 2 weeks 35-45 kg, after that transition to full-weight bearing (always only if possible)

- X-ray after 6 and 12 weeks; depending on the results, the schedule for weight bearing may be adjusted to the need in case of delayed healing or complications related to implants

Group 2 (treatment with 'Settner shoe'):

- mobilization with the custom-made heel-unloading orthosis ('Settner shoe') without pads for 6 weeks, then 2 weeks one pad, 2 weeks 2 pads, 2 weeks 3 pads, after that full-weight bearing without any support (always only if possible)
- X-ray after 6 and 12 weeks; depending on the results, the schedule for weight bearing may be adjusted to the need in case of delayed healing or complications related to implants

The patients of both groups are informed about the aftercare at the time point of inclusion.

Outcomes

Primary outcome criterion

The number of active minutes per day following 3 months (time point 2) is primary outcome criterion.

Secondary outcome criteria

- active minutes per day at time point 1
- portion of highly active periods per day at time point 1 and 2
- the EuroQol 5D-3L questionnaire following 3 months (time point 2)

Explorative outcome criteria

- AOFAS
- 3-dimensional gait analysis
- time point of return to work of patients between 18 and 60 years
- range of motion (ROM)
- Pro- and supination (percent of healthy side or assumed normal mobility) are analyzed.
- pain
- The evaluation includes the medication and a visual-analogue scale (VAS).
- comparison between patients with and without operation

Patient characteristics beside outcome criteria

Epidemiology

- age
- sex
- body mass index
- ASA (American Society of Anesthesiologists) physical status classification system

Injury characteristics

- classification according to Sanders (figure 4)
- classification of open/closed tissue damage (table 1)
- polytrauma (ISS \geq 16, multiple injuries, monitrauma)
- indication for operation (dislocation, broadening, flattening of Böhler angle etc.) or conservative therapy (comorbidity, smoking etc.)

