- the time between the fracture occurred and operation or decision making for non-operative therapy

[figure not shown]
Healing and treatment characteristics

- bone healing after 3 months: union or delayed healing
The decision is made based on conventional radiographs including the clinical description of complains.
- weight bearing after 3 months
Is it possible or not?
- hindfoot axis (varus/valgus-deformity, Böhler angle, subtalar osteoarthritis)
The decision is made based on conventional radiographs and a clinical evaluation.
- type of operation (approach, fixation method, graft)

Complications

- infection (I)
- deep venous thrombosis (DVT)
- nerve paresis/palsy/disturbed sensibility (N)
- subtalar posttraumatic osteoarthritis (PTOA)
- subtalar instability (SI)
- local mechanical irritation by plate/screws (LI)
- wound irritations (WI) as superficial healing problems or skin edge necrosis
- irritations associated to the use of the custom-made heel-unloading orthosis ('Settner shoe')

Participant timeline

The clinical and radiological controls correlate with the usual guidelines for treating calcaneus fractures at the Odense University Hospital.

Sample size and power analysis

The sample size calculation was based on a 33% difference in activity, correlating with a clinical relevant difference. Setting the power to 80% and the 2-sided confidence interval to 95% the calculation according to the method of Fleiss with continuity correction resulted in 25 patients per group.

Recruitment

All consultants of the trauma section of the Department of Orthopaedics and Traumatology at the University Hospital Odense are involved in the recruitment process of the study.

Methods: Assignment of interventions (for controlled trials)

Allocation

In the period between treatment (either decision-making for non-operative therapy or open reduction and internal fixation) and consolidation of the soft-tissue situation, the patients are randomized for the aftercare with or without the custom-made heel-unloading orthosis ('Settner shoe'). As soon as the soft-tissue situation allows the adjustment, the patients are referred to an orthopaedic shoemaker, who equips the patient accordingly. The randomization is done using the tool provided by OPEN.

Blinding (masking)

The allocation is not blinded, because it will be obvious to the patient, whether a special shoe is worn or not. Furthermore, the treating trauma surgeon needs to initiate the prescription.

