Measurement of physical activity

For monitoring of activity, the patients are equipped with a Misfit™ Shine (Burlingame, CA, USA) at the ankle and an Axivity™ AX3 (Newcastle upon Tyne, UK) at the lateral femur of the unaffected side. If there is a fracture at both sides, the trackers are attached to the side with the less complicated fracture. The wear time is 7 days. At day 7±14 (discharge) and after 3±0.5 months patients are equipped, and activity signals are analyzed by calculating the mean of all acquired 24-hour-data during these two periods. Regarding the Misfit™ Shine, only the number of registered steps is recorded. Regarding the Axivity™ AX3, the portion of highly active periods per day and the number of active minutes, correlating with walking activity, have shown to be most discriminating in the preliminary validation study. Therefore, these parameters are selected. Reliability is checked using a wear-time analysis based on change of signal vector magnitudes and temperature monitoring.

Correlating with these two data points, the EuroQol 5D-3L questionnaire [5] and the AOFAS [6] are monitored.

Classification

Classification of calcaneus fractures according to Sanders

[figure not shown]

Figure 3: Axial load is necessary for calcaneus fractures, which should be treated with a heel-unloading 'Settner shoe'.

[figure not shown]

Figure 4: The fracture classification according to Sanders can group the calcaneus fractures that occur following axial load [7].

Classification of open fractures according to Gustilo-Anderson

| Gustilo Grade | Definition |
|---------------|--|
| I | Open fracture, clean wound, wound <1 cm in length |
| II | Open fracture, wound > 1 cm but < 10 cm in length without extensive soft-tissue damage, flaps, avulsions |
| III | Open fracture with extensive soft-tissue laceration (>10 cm), damage, or loss or an open segmental fracture. This type also includes open fractures caused by farm injuries, fractures requiring vascular repair, or fractures that have been open for 8 hr prior to treatment |
| IIIA | Type III fracture with adequate periosteal coverage of the fracture bone despite the extensive soft-tissue laceration or damage |
| IIIB | Type III fracture with extensive soft-tissue loss and periosteal stripping and bone damage. Usually associated with massive contamination. Will often need further soft-tissue coverage procedure (i.e. free or rotational flap) |

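### The early EQ-5D-3L has no analytic role and may follow randomisation; completed before randomisation and used as a covariate, it may sharpen the 3-month quality-of-life comparison at little cost

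*Combined protocol and SAP*

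**What the plan says.** All references are to the combined protocol and SAP.

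- **Outcome.** Research questions lists quality of life second. Secondary outcome criteria includes "the EuroQol 5D-3L questionnaire following 3 months (time point 2"; no EQ-5D-3L outcome is listed at time point 1.
- **Collection.** Appendices, Measurement of physical activity, sets the two measurement occasions: "At day 7±14 (discharge) and after 3±0.5 months patients are equipped". It then adds: "Correlating with these two data points, the EuroQol 5D-3L questionnaire [5] and the AOFAS [6] are monitored". The questionnaire is therefore completed twice.
- **Analysis.** Statistical methods gives a general list: t-test, nonparametric tests, chi-square test and Spearman correlation. It names no covariate, change score or analysis of covariance, and it has no sentence specific to EQ-5D-3L.
- **Order of events.** Acquiring patient consent states: "Patients are included after the operation or after decision for non-operative therapy, but before discharge". Allocation places randomisation anywhere between treatment and recovery of the soft tissue. Interventions has patients in both arms told about their aftercare when they are included. Blinding (masking) confirms that allocation is open.

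**The concern.** A score taken before randomisation that predicts the 3-month score can serve as a covariate and reduce the unexplained variance. The plan already pays for an early EQ-5D-3L but does nothing with it.

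The early score also cannot simply be put into the model as it stands. It is tied to the tracker fitting and not to consent, so it may be answered when the patient already knows the arm or already wears the shoe. Adjusting for a score that the shoe could have influenced might remove part of the effect being estimated.

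At stake is the width of the confidence interval on one secondary outcome in a trial of 50 patients. The primary outcome, active minutes at 3 months, is not affected.

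**Working it through.** **1. Can the early score fall after randomisation?** The window of day 7±14 runs to day 7 + 14 = 21. If days are counted from treatment (the appendix does not say), that is the same 3 weeks that the exclusion criteria allow for fitting the shoe. Randomisation lies somewhere inside this period, and no sentence fixes its order relative to the first questionnaire. The score may precede randomisation, follow it, or follow the fitting.

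**2. The plan's own sample size.** Sample size and power analysis reports that "the calculation according to the method of Fleiss with continuity correction resulted in 25 patients per group", for a 33% difference in activity with 80% power and a two-sided 5% level. Taking the proportions as 100% and 67% (an assumption; the plan gives none):

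- Uncorrected: n = [1.96·√(2·0.835·0.165) + 0.8416·√(0.67·0.33)]² / 0.33² = (1.029 + 0.396)² / 0.1089 = 18.6, so 19.
- With continuity correction: n = (18.6/4)·[1 + √(1 + 4/(18.6·0.33))]² = 24.3, so 25.

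The 25 is reproduced. It concerns activity and says nothing about power for EQ-5D-3L, for which the plan gives neither a standard deviation nor a target difference. The steps below therefore work in SD units, with 25 per arm and no dropout (the plan states none).

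**3. Effect of adjustment.** Let r be the correlation between the pre-randomisation and 3-month index. The documents do not give it; 0.1 to 0.5 is assumed.

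- Large-sample variance factor of analysis of covariance: 1 − r².
- Expected cost of estimating the slope when the covariate is imbalanced by chance: 1 + 1/(N − 4) = 1 + 1/46 = 1.022 at N = 50.
- Variance factor used: 1.022·(1 − r²). Equivalent patients per arm: 25 divided by that factor. Change in CI width: its square root minus 1.
- Power at 0.81 SD, the difference that gives 80% unadjusted by the t-test: noncentral t with 47 degrees of freedom and noncentrality (0.81/√factor)·√(25/2).

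| Assumed r | Variance factor | CI width | Equivalent n per arm | Power at 0.81 SD |
|---|---|---|---|---|
| 0.1 | 1.022·0.99 = 1.01 | +1% | 24.7 | 79.5% |
| 0.2 | 1.022·0.96 = 0.98 | −1% | 25.5 | 80.7% |
| 0.3 | 1.022·0.91 = 0.93 | −4% | 26.9 | 82.7% |
| 0.4 | 1.022·0.84 = 0.86 | −7% | 29.1 | 85.6% |
| 0.5 | 1.022·0.75 = 0.77 | −12% | 32.6 | 89.2% |

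Break-even: 1 − r² = 1/1.022, so r = √0.021, about 0.15.

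**4. Why not a change score?** With equal variances at both times, its variance relative to the 3-month score alone is 2(1 − r): 1.4 at r = 0.3, 1.2 at 0.4 and 1.0 at 0.5. Below r = 0.5 it is worse than no adjustment.

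**The case against.** The strongest reply is that nothing here is wrong. Randomisation makes the comparison of 3-month scores valid without a baseline. A reader might infer that, for want of a baseline, a chance difference in starting health cannot be told apart from the effect of the shoe. The documents do not support that: the confidence interval and p-value of the unadjusted comparison already allow for chance imbalance. A reader might also infer that adjustment would remedy the open-label design. It would not, because it does nothing about reporting bias in a 3-month questionnaire answered by patients who know their arm. Both replies stand.

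The gain may also be nil. Every patient has a recent calcaneus fracture at inclusion, so a three-level questionnaire may vary little between patients and r may be low. This stands, and is why 0.1 and 0.2 are in the table. The possible loss is small: 79.5% against 80% power at r = 0.1.

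That the 3-month score is compared unadjusted is an inference from the general methods paragraph. This stands too, although no other analysis is described.

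Finally, moving the first questionnaire separates it from the time point 1 activity and AOFAS data, which could matter for the planned correlations. That is a real cost, but the plan specifies no correlation that uses the early EQ-5D-3L.

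**Conclusion.** The point holds as a cheap improvement. The early EQ-5D-3L has no analytic role, and as scheduled it may follow randomisation, so it should not be used as a covariate without a change in timing. The existing comparison is valid; the possible loss is precision on research question 2.

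The gain is likely but of unknown size. It ranges from a 1% increase in variance at r = 0.1 to a reduction of about 23% at r = 0.5, with break-even near 0.15. These figures assume 25 analysed patients per arm, a linear relation and a correlation that the documents do not give.

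A reader might conclude that moving the questionnaire to inclusion is enough. It is not: randomisation is not tied to inclusion, and patients are told about their aftercare at that point. Only an explicit order, with the score before randomisation and before disclosure of the arm, makes it a baseline.

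**What to change.** In Appendices, Measurement of physical activity, add:

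> *The first EQ-5D-3L is completed after consent and before randomisation and before the patient is told the aftercare arm.*

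In Statistical methods, add:

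> *The EQ-5D-3L index at time point 2 is compared between arms by analysis of covariance with the pre-randomisation index as covariate, reporting the adjusted mean difference with 95% CI; if residuals are clearly non-normal, a rank-based analysis of covariance is used.*

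The plan does not say which EQ-5D-3L score is analysed, so the sponsor should also name the value set for the index.

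For patients already enrolled, use the first score only if it predates randomisation. Otherwise impute the mean pooled over both arms; this keeps the patient in the model but restores no precision for that patient. The change should be fixed before outcome data are examined.

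**Cost.** An existing short questionnaire moves by days, and two sentences are added. No new visit or instrument is needed: inclusion already takes place before discharge, and patients must be able to answer the questionnaires to be eligible. The analysis spends one degree of freedom, and the first EQ-5D-3L is no longer taken together with the time point 1 activity and AOFAS measurements.
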